3 INVESTIGATIONAL PLAN

3.1 Study Design

This is a multiregional, multicenter, Phase 2, randomized, observer-blind study performed in younger and older adult participants. Enrolled participants will be randomly assigned to receive either study vaccine (ARCT-021 or placebo [0.9% sterile saline]) as the priming vaccination series or ARCT-021, ARCT-154, ARCT-165, or placebo as the booster administration. This study will evaluate the safety, reactogenicity, and immunogenicity of the study vaccine in younger and older adult participants.

Approximately 600 participants will be stratified by age group (300 each in younger (≥ 18 to <56 years of age or ≥ 21 to <56 years of age if in Singapore) and older (≥ 56 years of age). At Day 0, participants will be stratified by age and then randomly assigned (ARCT-021:placebo in a ratio of 3:1) to receive 2 doses of study vaccine separated by 28 days and at Day 208, participants will be randomly assigned to ARCT-021, ARCT-154, ARCT-165, or placebo (for Study Groups 1, 2, 3 only) for a third (booster) dose of study vaccine given at 180 days after second study vaccination (Day 208). The randomization ratio of ARCT-021, ARCT-154, ARCT-165, placebo will be 1:1:1:1 for Study Groups 1, 2, 3 and the randomization ratio will be 1:1:1 for ARCT-021, ARCT-154, ARCT-165 (no placebo assignment) for any remaining participants in Study Group 4.

Participants who complete study procedures through Day 98 will be offered the opportunity to determine whether they are eligible for study re-enrollment to ensure dosing with ARCT-021. Participants may also seek an approved COVID-19 vaccine, if available locally and recommended by local authorities.

Study vaccine will be administered in an observer-blind fashion.

With Protocol Version 6.0, the last study vaccine doses are intended for administration by 15 December 2021 and participants will be followed for safety and immunogenicity through at least 56 days after last vaccination. The last study visit will be an Early Termination visit rather than Final Visit.

The total study participation for each participant would be described as follows:

- Total participation of up to Day 353 for participants who did not enroll and who received booster vaccine;
- Total participation of up to Day 396 for participants who did not re-enroll and who did not receive booster vaccine;
- Total participation of up to Day 264 after re-enrollment.

[figure not shown]

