9.1.2. Unsolicited Adverse Events

Unsolicited AEs that meet the protocol definition of MAAE, NOCD, SAE, AEs leading to delay in dosing of the next vaccine, or AEs leading to termination of vaccine dosing will be captured for the duration of study participation. NOCD are defined as a subset of MAAEs that are specific to new onset of chronic diseases not otherwise suggested or suspected prior to entry into the study. Continuing solicited AEs after 7 days will be captured as unsolicited AEs and followed until stabilization/resolution.

Only treatment emergent adverse events (TEAEs) will be included in summary tables. Percentages will be based upon the number of participants in the Safety analysis set within each treatment group. A participant with 2 or more AEs within the same level of summarization (e.g., SOC or PT) will be counted only once in that level.

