9.1.2.2. Unsolicited AEs by Time Period

Summaries of unsolicited AEs by time period will be presented using the following definition:

- **Prior to Booster Vaccination** summary tables include the following time periods with data summarized by the 4 priming vaccination treatment groups:
 - **Vaccination 1 through prior to Vaccination 2:**

- For participants who receive vaccination 2, this is the time period from first vaccination through prior to second vaccination
- For participants who do not receive vaccination 2 but do receive a booster vaccination, this is the time period from first vaccination through prior to the booster vaccination
- For participants who only received the first vaccination, this is the time period from first vaccination until early termination or end of the priming period (Day 207), whichever is earlier
- **Vaccination 2 through prior to Booster Vaccination:**
 - For participants who receive the booster vaccination, this is the time period from the second vaccination through prior to the booster vaccination
 - For participants who do not receive the booster vaccination, this is the time period from second vaccination until early termination or end of the priming period (Day 207), whichever is earlier
- **Prior to Booster Vaccination - Overall**
 - This is the time period from first vaccination through prior to booster vaccination. For participants who do not receive a booster vaccination, this is the time period from first vaccination through early termination or end of the priming period (Day 207), whichever is earlier.
- **Post Booster Vaccination through Early Termination** summary tables include data summarized by the 8 priming-booster treatment groups as well as a summary for the combined E1+E2+...+G1+G2 and H1+H2 groups. For subjects who do not receive a booster vaccination, this is the time period from the start of the booster period (Day 208) through early termination.
 - An overall summary of unsolicited adverse events post booster vaccination with active boosters pooled (as presented in Table 4-1; e.g., A1, A2, B1, B2, etc.) will also be presented.

The summaries described in [Section 9.1.2.1](#) will be produced by time period and by time period and age group. In addition, the following summaries will be presented by time period and by time period and age group:

- Overall summary and incidence of treatment emergent MAAE
- Overall summary and incidence of treatment emergent NOCDs

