9.4. COVID-19 exposure and symptoms

The number and percentage of participants reporting symptoms of potential COVID-19 (Yes/No/missing) from CRF page SARS-CoV-2 or COVID-19 Symptoms Assessment will be summarized by treatment groups for the Safety analysis set. For participants reporting ‘Yes’, all symptoms will also be summarized by frequency.

For participants identified as on-study infection, the number and percentage of participants reporting ‘Yes’ to the question Any Symptom of Confirmed COVID-19 from CRF page Clinical Event of Special Interest will be reported by treatment groups and by each priming vaccination period. All symptoms will also be summarized by frequency.

Incidence of COVID-19 and incidence of asymptomatic infection based on the Adverse Event CRF page will be summarized for the following time periods: after first study vaccine dose to 14 days after first study vaccine dose, between 14 days after first study vaccine dose to 2nd study vaccine dose, and after 2nd study vaccine dose to booster vaccine / early termination prior to Day 208 visit. This will also be summarized for re-enrolled subjects separately.

Incidence of COVID-19 and incidence of asymptomatic infection after booster vaccine to early termination after booster vaccine based on the Adverse Event CRF page will be summarized. For subjects not receiving a booster vaccination, events from Day 208 through early termination will be summarized under the Booster Placebo/No Booster group.

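### Post-booster event tables count unboosted participants from Day 208 but boosted participants from the injection, so control and active columns can cover different lengths of follow-up

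*SAP*

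**What the plan says.** SAP 9.1.2.2 defines a set of tables headed "Post Booster Vaccination through Early Termination". They are laid out by the eight priming-booster groups of SAP Table 4-1, by all active boosters combined against H1+H2, and in a version with active boosters pooled within priming group. For those "who do not receive a booster vaccination, this is the time period from the start of the booster period (Day 208) through early termination". The bullet gives no explicit start for boosted participants. The same section assigns their earlier time to the pre-booster tables: "this is the time period from the second vaccination through prior to the booster vaccination". Unboosted participants are cut off in those tables at Day 207 at the latest.

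SAP 4.4.9 puts an unboosted participant who has booster-period safety data into the placebo booster group. In Table 4-1, H1 (and A2, B2, C2 in the pooled layout) mixes placebo-boosted with unboosted participants, while H2 and D2 contain only unboosted ones. On the measure, SAP 9.1.2 says "Percentages will be based upon the number of participants in the Safety analysis set within each treatment group". No person-time is planned.

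SAP 9.4 repeats the rule for infection: "For subjects not receiving a booster vaccination, events from Day 208 through early termination will be summarized under the Booster Placebo/No Booster group".

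The booster visit window is +60 days (Protocol Table 13-2, and the booster schedule in SAP Appendix 1). Protocol 3.1 gives the participation limits: "Total participation of up to Day 353 for participants who did not enroll and who received booster vaccine" (taken here to mean did not re-enroll) and "Total participation of up to Day 396 for participants who did not re-enroll and who did not receive booster vaccine".

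**The concern.** A crude percentage rises with the length of time over which events are counted. If one column of a table counts from Day 208 and its neighbour from an injection that may come weeks later, the two can differ with no true difference in risk. A longer window in the control column could mask an excess of medically attended, serious or new chronic events after an active booster, or make a booster look protective against COVID-19. A shorter one would do the reverse.

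This matters because the tables include ARCT-154 and ARCT-165, for which Protocol 1.5 reports no clinical trials as of Investigator's Brochure version 4.0, and because booster groups may be as small as 25 (SAP 4.2). The plan also provides for an unboosted group. Under Protocol 4.2.3, participants who decline the booster may stay in the study, and those who take an off-study COVID-19 vaccine get no further study doses but are invited to continue to Early Termination.

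**Working it through.** **1. The boosted start.** The table title says post booster, and time up to the injection belongs to the pre-booster tables. The two periods are complementary, so the boosted clock starts at the injection. This is an inference, but no other reading fits both definitions.

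**2. The plan's own follow-up figure.** The last booster date is 15 December 2021 and the target end is 16 February 2022 (Protocol synopsis): 16 days to 31 December + 31 + 16 = 63 days. This agrees with the stated minimum of 56 days after the last vaccination.

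**3. Effect of the clock rule alone.** Take the same enrolment date and end date, so that only the start differs. Gap = booster day − 208.

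| Case | Unboosted window | Boosted window | Ratio |
|---|---|---|---|
| Booster on Day 208, end Day 353 | 353 − 208 = 145 | 353 − 208 = 145 | 1.00 |
| Booster on Day 268, end Day 353 | 145 | 353 − 268 = 85 | 1.71 |
| Booster on Day 268 (15 Dec 2021), end 16 Feb 2022 | 63 + 60 = 123 | 63 | 1.95 |

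The gap is 0 to about 60 days. The Day 208 target follows the actual Day 28 visit, which has its own ±3 days, so the limits can shift by about 3 days.

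**4. A separate difference.** The participation limits give 396 − 208 = 188 days for unboosted and 353 − 208 = 145 for boosted participants. These 43 days come from different maximum participation, not from the clock rule.

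**5. What unequal windows do to a crude percentage.** The documents give no background rate, so assume one constant hazard for everyone, set by a 28-day risk r: h = −ln(1 − r)/28 and P(w) = 1 − exp(−h × w).

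| Assumed r | 63 days | 123 days | 85 days | 145 days |
|---|---|---|---|---|
| 1% | 2.2% | 4.3% | 3.0% | 5.1% |
| 2% | 4.4% | 8.5% | 5.9% | 9.9% |
| 5% | 10.9% | 20.2% | 14.4% | 23.3% |

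**6. Dilution in a mixed column.** Placebo-boosted participants in H1 share the injection clock. With r = 5%, 63 against 123 days and an unboosted share s, the column reads s × 20.2% + (1 − s) × 10.9%. For s = 25%, 50%, 75% and 100% this is 13.2%, 15.5%, 17.9% and 20.2%, against 10.9% in the active columns. The documents do not give s.

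**7. Masking, at the limit.** In a fully unboosted column with r = 5% and every booster at +60, a doubled hazard after active booster gives 1 − exp(−2h × 63) = 20.6%, against 20.2% in the control column.

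Steps 5 to 7 show the mechanism under assumed rates and the longest permitted delay. They are not estimates of what the tables will show.

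**The case against.** The case for leaving the tables alone has real content. The booster objectives are exploratory, no hypotheses are tested, and SAP Section 1 already warns that interpretation may be limited beyond Day 56. SAP 9.1.2.1 has a fixed 28-day post-booster table by all eight groups, and SAP 9.1.1 a 7-day reactogenicity window. The three active boosters and the injected placebo recipients share one clock in every table. All of that stands, and it bounds the point to the unboosted participants. It does not remove it. The 28-day table defines no window for the unboosted participants in H1 and H2, and the follow-up-length table in SAP 5.1 is by priming group, so it cannot show an imbalance between booster columns.

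A reader might infer that the control column always has the longer window and so systematically hides harm. The documents do not support that. The clocks coincide for a booster on Day 208, and unboosted participants who leave soon after Day 208 have short windows. General unsolicited AEs are prompted only to 28 days after a dose (Protocol synopsis), so rows for all unsolicited AEs could be biased the other way.

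A reader might also take 188 against 145 days, or 188 against the 63 days of the last permitted booster, as the size of the effect. The first contrast is not caused by the clock rule. The second sets the earliest unboosted participant against the latest boosted one, whereas the percentages depend on typical follow-up. Nor can 188 unboosted days be paired with a Day 268 booster followed to Day 396, because the protocol limits boosted participation to Day 353.

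**Conclusion.** The point holds in bounded form. As written, SAP 9.1.2.2 and 9.4 set crude percentages side by side over windows that start at different times. The rule alone contributes 0 to about 60 days per unboosted participant for a given enrolment and end date, up to 1.71 or 1.95 times the boosted window in the two worked cases. It fully affects H2 and D2, and H1, A2, B2 and C2 in proportion to their unboosted share. It applies mainly to events collected through Early Termination: MAAEs, NOCDs, SAEs, AEs leading to discontinuation, and COVID-19 or asymptomatic infection. The pre-booster tables carry the opposite imbalance, because boosted participants keep contributing after Day 207 until the injection.

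The realised imbalance and its net direction are unknown, since the unboosted share, the booster delays and the event hazards are not in the documents. The conclusion rests on the inferred boosted start and on the +60-day window being used.

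**What to change.** In SAP 9.1.2.2 and 9.4:

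- Show unboosted participants in their own column, separate from injected placebo.
- Make the active against placebo booster comparison among injected ARCT-primed participants, counted from the injection over one common window. Fifty-six days, the protocol's stated minimum follow-up, is a natural example. It should be censored at Early Termination if that comes earlier, because SAP Section 1 ends follow-up at 56 days or February 2022, whichever came first, and SAP 5.1 has a category for 56 days or less.
- In the through-Early-Termination tables, add events per person-time: participants with an event divided by total person-days from each participant's own clock start to first event or Early Termination.
- State the boosted start explicitly.

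The cost is SAP wording and a few extra table columns, from dates already collected. Events after the common window appear only in the person-time table. Person-time rates compare fairly only if the hazard is roughly constant, which is doubtful for COVID-19 over calendar time, so they should be read as description.

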Protocol ARCT-021-04, Version 6.0

ARCT-021
09 March 2022

Additional Procedural Specifics:

Solicited AEs will be evaluated by the participant and will include measurement of body temperature by thermometer and injection site reaction (erythema or induration/swelling) measurement by ruler. Both instruments and training on how to use them will be provided by the site.

An electronic Diary (eDiary) will be used to collect the following:

- Solicited local and systemic AEs through 7 days following each study vaccination
 - Solicited local AEs: injection site erythema, injection site pain, injection site induration/swelling, injection site tenderness
 - Solicited systemic AEs: arthralgia, chills, diarrhea, dizziness, fatigue, fever (categorized by measured body temperature), headache, myalgia, nausea/vomiting
 - Also solicited but not categorized as AE: antipyretic and analgesic use following vaccination
- Prompts for unsolicited AEs through the Early Termination. Prompts will solicit for all unsolicited AEs through 28 days after each vaccination and for unsolicited AEs categorized as SAEs, MAAEs, NOCDs, and AEs leading to discontinuation/withdrawal through Early Termination Visit.
- Prompts for symptoms of or exposure to COVID-19 disease from 7 days after first study vaccine administration through Early Termination Visit.

Blood sampling will be performed to collect:

- Laboratory assessments for Screening (a list of laboratory parameters is provided in [Appendix 2: Clinical Laboratory Tests](#))

All participants:

- Neutralizing antibody assessments for SARS-CoV-2 virus by pseudoviral microneutralization assay (Wuhan-Hu-1 [D614G strain]). Binding antibody assessments for SARS-CoV-2 including full-length spike, receptor binding domain (RBD) and nucleocapsid (N)-binding by Meso Scale Discover (MSD) multiplex assay. In some or all participants, additional exploratory antibody responses, including exploration of responses to SARS-CoV-2 variant strains, may also be evaluated if the blood and assays are available.

CMI subset of participants:

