7.1 Estimands and Intercurrent Events

Possible intercurrent events are presented in [Table 7-1](#).

Table 7-1 Intercurrent Event Types

Label	Intercurrent Event (IcEv) Type
IcEv1 (Death)	Death due to any cause (including pneumonia) other than COVID-19.
IcEv2 (Missed dose)	Does not receive the second or booster vaccinations at Day 28 and Day 208, respectively.
IcEv3 (Immune-modifying)	Use of immune-modifying drugs or non-study vaccines which interfere with immunogenicity.
IcEv4 (Early infection)	Antigens or antibodies indicating exposure to SARS-CoV-2 prior to vaccination or early infection before Day 7. (This IcEv is particularly relevant to assessing immunogenicity.)
IcEv5 (Study infection)	Develops COVID-19 or asymptomatic SARS-CoV-2 infection on or after Day 7. (This IcEv is particularly relevant to immunogenicity and CESI events.)

Attributes for the primary safety and immunogenicity estimands with strategies for intercurrent events (IcEvs) are presented in [Table 7-2](#).

Table 7-2 Primary Safety and Immunogenicity Estimands With Rationale and Strategies to Address Intercurrent Events

Estimand Label	Estimand 1 (Safety)
Estimand Description	Count and percentage of vaccinated healthy adults who would develop MAAEs, NOCDs, SAEs, AEs leading to discontinuation/withdrawal, solicited AEs, and unsolicited AEs: These will be evaluated after each dose of study vaccine by priming vaccine study group (Group 1, 2, 3, and 4) and by booster vaccine received (ARCT-021, ARCT-154, ARCT-165, or placebo). A treatment policy strategy is used for assessing safety irrespective of an early infection within 7 days after the first vaccination or an infection during the study or missed subsequent vaccination. Infections and death are included in the endpoint (composite strategy).
Target Population	Participants receiving at least 1 dose of study vaccine (as defined by eligibility criteria).
Endpoint	Occurrence of MAAEs, NOCDs, AEs leading to discontinuation/withdrawal, SAEs, solicited, or unsolicited AEs: 
 Solicited AEs within 7 days of each vaccination (by Toxicity Grade, Appendix 13.4): Day 7, Day 35, Day 215 Unsolicited AEs within 28 days of each vaccination (by mild/moderate/severe severity): Day 28, Day 56, Day 236 MAAEs, NOCDs, SAEs, AEs leading to discontinuation/withdrawal from Vaccination 1 to Prior to Vaccination 2, Vaccination 2 to Prior to Booster Vaccination, Overall Prior to Booster Vaccination, and Post-booster Vaccination

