7.6.2 Overview of Statistical Methods: Estimation of Estimands and Sensitivity Analyses

A summary of the statistical methods and sensitivity analyses is presented in [Table 7-4](#). Placebo participants will be pooled across dose groups summaries.

Table 7-4 Summary of Statistical Methods and Supportive Analyses

Estimand Label	Estimand Description	Main Estimation			Supportive Analysis
		Analysis Set	Imputation/ Data/ Censoring Rules	Analysis Model/Method	
Estimand 1 (Primary)	
Percentage of vaccinated healthy adults who:
 
 report solicited AEs within the specified timeframe develop unsolicited AEs including MAAEs, etc, within the specified timeframe. 
A treatment policy strategy is used for assessing safety irrespective of a current (or prior) infection at time of first vaccination or missed second vaccination. See Table 7-2 for full definition.
	RAS (solicited AEs) SAS (unsolicited AEs)	Infections and death (if they meet the AE and time window criteria) are included in the endpoint (composite strategy).	Summaries of number of participants (%) with solicited AEs (by toxicity grade), safety laboratory assessments (by toxicity grade), unsolicited AEs (by severity and relatedness to study vaccine), MAAEs, NOCDs, SAEs, and AEs leading to discontinuation/withdrawal will be presented. The Clopper-Pearson 95% CIs will be presented for the incidence rate of these events. See Section 7.6.3.1 and the SAP for further details.	
Supportive: Analysis will be performed for a number of different time intervals, specifically:
 
 Solicited AEs: within 7 days of first vaccination and also within 7 days after each vaccination Safety laboratory assessments 7 days before and after each vaccination Unsolicited AEs: within 28 days of each vaccination (Days 28, 56, 236) All unsolicited AEs, MAAEs, NOCDs, SAEs, AEs leading to discontinuation/withdrawal up to by time period after the first vaccination Additional supportive analyses are defined in the SAP

Table 7-4 Summary of Statistical Methods and Supportive Analyses

Estimand Label	Estimand Description	Main Estimation			Supportive Analysis
		Analysis Set	Imputation/ Data/ Censoring Rules	Analysis Model/Method	

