9.1.2.1. Unsolicited AEs through 28 Days Post Each Vaccination

Summaries of unsolicited AEs through 28 days post each vaccination dose will be presented using the following definition:

- **Vaccination 1:** Time period from first vaccination through prior to the second vaccination for participants that received the second vaccination and through 28 days following the first vaccination for participants that did not receive the second vaccination
- **Vaccination 2:** Time period from second vaccination through 28 days following the second vaccination
- **Booster Vaccination:** Time period from booster vaccination through 28 days following the booster vaccination.

The summaries for Vaccination 1 and Vaccination 2 will be by the 4 priming vaccination treatment groups for the priming vaccination period while the summaries for booster vaccination period will be by the 8 priming-booster vaccination treatment groups and for the combined E1+E2+...+G1+G2 and H1+H2 groups (Table 4-1).

For re-enrolled subjects, the above summary for the priming vaccination phase will be repeated.

An overall summary of unsolicited AEs through 28 days post vaccination will be produced for all participants and by age group including the number and percentage of participants with any of the following (including 2 sided 95% CIs using the Clopper-Pearson method):

- Any unsolicited TEAEs
- Any severe unsolicited TEAEs
- Any unsolicited TEAEs that are treatment related

- Any severe unsolicited TEAEs that are treatment related
- Any serious TEAEs
- Any treatment-emergent MAAEs
- Any treatment-emergent NOCDs
- Any TEAEs leading to discontinuation/withdrawal
- Any TEAEs leading to death

In addition, incidence of unsolicited AEs through 28 days post each vaccination will be summarized by SOC and PT including number and percentage of participants with an event for all participants and by age group for the following:

- All unsolicited AEs
- All unsolicited AEs by severity
- All unsolicited AEs by relationship to treatment

For re-enrolled subjects, the above summaries will be repeated for the Safety set. A summary of incidence of unsolicited adverse events up to 28 days post booster vaccination with active boosters pooled will be presented.

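### SAP 9.1.2.2 tabulates all unsolicited AEs over periods far longer than the 28 days in which ordinary AEs are prompted, and never-boosted participants have no prompted window after Day 208

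*SAP*

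**What the plan says.** **What is tabulated.** SAP 9.1.2.1 defines tables of any, severe and related unsolicited TEAEs, and adds that "incidence of unsolicited AEs through 28 days post each vaccination will be summarized by SOC and PT", also by severity and relationship. SAP 9.1.2.2 then states that these summaries "will be produced by time period and by time period and age group". For a participant with two doses and no booster, the second priming period is defined as follows: "this is the time period from second vaccination until early termination or end of the priming period (Day 207), whichever is earlier". After that, for someone without a booster, "this is the time period from the start of the booster period (Day 208) through early termination". Protocol Table 7-4 lists the same thing as supportive: "All unsolicited AEs, MAAEs, NOCDs, SAEs, AEs leading to discontinuation/withdrawal up to by time period after the first vaccination". Protocol 7.6.3.2 also applies the main safety analyses, which include unsolicited AEs, to the same named periods.

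**What is collected.** The protocol synopsis says of the diary: "Prompts will solicit for all unsolicited AEs through 28 days after each vaccination". Protocol Section 6 has a similar 28-day rule. Protocol 6.4.1.2 names MAAEs, NOCDs, SAEs and AEs leading to withdrawal or discontinuation as captured throughout. SAP 9.1.2 says of a similar list, worded in terms of delayed or terminated dosing, that these events "will be captured for the duration of study participation".

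**What the estimand asks for.** Estimand 1 (Protocol Table 7-2, SAP Table 13-4) gives ordinary unsolicited AEs a 28-day window. It reserves the long periods for the special classes: "MAAEs, NOCDs, SAEs, AEs leading to discontinuation/withdrawal from Vaccination 1 to Prior to Vaccination 2", and so on through the later periods.

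**Where unboosted participants go.** In SAP Table 4-1, H2 and D2 are wholly no-booster groups, while H1, A2, B2 and C2 mix placebo-booster and no-booster participants. SAP 4.4.9 places unboosted participants with booster-period safety data with the placebo booster group.

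**The concern.** A percentage with any unsolicited AE over one of these periods mixes 28 (or 56) days of prompted reporting with a much longer stretch in which ordinary AEs are recorded at an unknown rate. It estimates no defined risk.

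Within the priming arms this is mainly a labelling problem, since all four arms have the same windows. After Day 208 it becomes a comparison problem. A boosted participant starts the period with 28 prompted days and a never-boosted participant starts with none, yet SAP 9.1.2.2 shows them in adjacent columns and sets the combined E1 to G2 groups beside H1+H2. H2 is the only placebo-primed comparator for E2, F2 and G2. A difference in ordinary AEs could therefore come from how events were sought. The SAP gives no onset cut-off, person-time rate or footnote that would let a reader tell.

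**Working it through.** **1. The plan's own windows.** Dose 1 on Day 0: 0 + 28 = Day 28. Dose 2 on Day 28: 28 + 28 = Day 56. Booster: 28 + 180 = Day 208, and 208 + 28 = Day 236. These match the Day 28, 56 and 236 window ends in Protocol 7.6.3.2.

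**2. Prompted share of each period.** Inputs are the periods in SAP 9.1.2.2, the +60-day booster window in Protocol Table 13-2, and the follow-up limits in Protocol 3.1 (at least 56 days after the last vaccination; up to Day 353 if boosted, up to Day 396 if not boosted and not re-enrolled).

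| Period | Prompted days / length | Share |
|---|---|---|
| Vaccination 2 to booster, nominal | 28/180 | 15.6% |
| Same, booster 60 days late | 28/240 | 11.7% |
| Overall pre-booster, nominal | 56/208 | 26.9% |
| Same, booster 60 days late | 56/268 | 20.9% |
| Post-booster, boosted, shortest | 28/56 | 50% |
| Post-booster, boosted, longest (353 − 208 = 145) | 28/145 | 19.3% |
| Day 208 onward, never boosted, longest (396 − 208 = 188) | 0/188 | 0% |

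**3. Effect on the boosted v no-booster display.** The documents give no background rate, so this is an illustration. Assume a risk p of at least one ordinary AE per 28 days, a constant hazard, no booster effect, and a fraction c of ordinary AEs outside the prompted window being recorded anyway. Then:

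- boosted, followed T days: 1 − (1 − p)^((28 + c(T − 28))/28)
- never boosted, followed U days: 1 − (1 − p)^(cU/28)

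With p = 10%, T = 56 to 145 and U = 188:

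| c | Boosted | Never boosted |
|---|---|---|
| 0 | 10% | 0% |
| 10% | 11% to 14% | 7% |
| 25% | 12% to 19% | 16% |
| 50% | 15% to 28% | 30% |
| 100% | 19% to 42% | 51% |

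The pattern is the same at other backgrounds. At p = 5%, c = 10% gives 5.5% to 7.0% v 3.4%, and c = 50% gives 7.4% to 14.7% v 15.8%. At p = 20% the corresponding figures are 22% to 27% v 14%, and 28% to 50% v 53%.

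**4. What drives the reversal.** At equal follow-up T, the boosted exponent exceeds the unboosted one by [28 + c(T − 28)] − cT = 28(1 − c) days, which is never negative. So the direction reverses only where never-boosted participants are followed longer, as Protocol 3.1 allows. If they were followed only 63 days (15 December 2021 to 16 February 2022), c = 50% would give 11%, below the boosted range.

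**5. Dilution in the pooled column.** With c = 0 and an assumed half of a pooled placebo/no-booster column never boosted, that column shows 2.5%, 5% and 10% for p = 5%, 10% and 20%, against 5%, 10% and 20% in boosted participants.

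**6. Truncation in the priming period.** With c = 0, Vaccination 2 to booster shows 5%, 10% and 20% for those backgrounds. Full capture over 180 days would show 28%, 49% and 76%.

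**The case against.** The strongest reply is that the protocol does not confine ordinary AEs to 28 days. Section 6.4.1.1.1 makes the investigator responsible for all AEs observed or reported during the study. Section 6.4.1.2 has AEs assessed until study exit, with a non-leading question at every visit. Section 6.4.1.3 has all unsolicited AEs recorded on the eCRF. Tables 13-1 and 13-2 schedule AE review at every visit and call from first dosing. The 28-day rule governs diary prompts, which are one channel. This stands: a reader might infer that ordinary AEs are captured only for 28 days, and the documents taken together do not say so. They leave the collection rule unreconciled.

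A reader might also infer that never-boosted participants must look falsely safer. That follows only if late recording is low. Confirmed COVID-19 and asymptomatic infection are also entered as AEs and followed to Early Termination, so the unboosted rate for any unsolicited AE need not be near zero even then.

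The scope is also limited. Placebo-booster recipients have the same 28-day window as active-booster recipients, so that randomised contrast suffers only dilution where never-boosted participants are pooled in. Boosted v unboosted is not a randomised comparison. The 28-day tables and separate period tables for the special classes are already planned, and the analysis is descriptive.

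None of this makes the long-period ordinary-AE rows interpretable. If late events are partly recorded, the percentage mixes prompted and unprompted reporting in unknown proportion.

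**Conclusion.** The point holds as one of unequal and undefined ascertainment. SAP 9.1.2.2 tabulates ordinary unsolicited AEs over periods of which roughly 16% (Vaccination 2 to booster), 27% (overall pre-booster) and 19% to 50% (post-booster, boosted) are prompted, against 0% after Day 208 in never-boosted participants. The boosted v no-booster percentages for these rows cannot be read as a safety contrast. Their size and direction depend on a late-recording rate that neither document states, and on follow-up that can be longer without a booster.

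The shares are arithmetic on the documents' own days. The illustrative risks rest on an assumed background of 5% to 20% per 28 days, a constant hazard and no booster effect. They show that the direction is not fixed; they do not predict a result.

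The priming-arm comparisons, the contrast between recipients of active and placebo booster, the special-class rows and Estimand 1 show no evident bias from this. It should be corrected, but it does not threaten the primary safety analysis.

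**What to change.** - In SAP 9.1.2.2, restrict the time-period tables to SAEs, MAAEs, NOCDs, AEs leading to discontinuation or withdrawal, and deaths, consistent with Estimand 1. Alternatively, keep the other rows but count only events with onset within 28 days after a dose.
- Keep never-boosted participants out of the all-unsolicited-AE columns, or show them separately from placebo-booster recipients.
- Align Protocol Table 7-4 and Protocol 7.6.3.2. Changing the SAP alone would create a new conflict.
- Reconcile Protocol 6.4.1.1.1, 6.4.1.2 and 6.4.1.3 with the 28-day prompting rule in the synopsis and Section 6 and with SAP 9.1.2, and state how ordinary AEs after 28 days were recorded.

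The cost is wording and fewer summary tables. Ordinary AEs arising after 28 days, including severe or related ones outside the special classes, would appear only in the listings that SAP 9.1.2.2 already plans.
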